3.1 Primary objective and endpoint

The primary objective is to demonstrate superiority of Perlane-Lido relative to no-treatment in the treatment of Midface volume Deficit and/or Midface Contour Deficiency by comparing the percent responders, defined by at least 1 point improvement from baseline on the MMVS on both sides of the face, as measured by blinded evaluator at 6 months.

CCI

 GALDERMA	Title 43CH1507 Perlane Lido midface study protocol	Doc id MA-30843
--	---	----------------------------------

CCI

3.3 Safety objectives and endpoints

The safety objectives and endpoints are:

- To evaluate the safety of Perlane-Lido during the whole study by collecting Adverse Events (AEs).

CCI

4 Design of the Study

4.1 General Outline

This is a randomized, evaluator-blinded, no-treatment controlled study in subjects with Midface Volume Deficit and/or Midface Contour Deficiency.

Subjects will be screened for eligibility within 21 days prior to Baseline. The first 2 eligible subjects for each Treating Investigator will receive treatment as Group A. Before start of enrolment into Group B, the injection technique will be evaluated by the Sponsor and performed when the subjects in Group A for each site have received their first treatment. If treatments are found to be correctly performed, no further training is needed, there are no outstanding questions regarding the injection technique and no other corrective actions are identified, the enrolment in Group B can start for that site. Subjects in group B will be randomized either to the Treatment Group or the Control Group in a 3:1 ratio.

Summaries of the results for Group A and B will be done separately in the study report.

Treatment

Each subject assigned to Group A or the Treatment Group in Group B will receive an initial treatment on Day 1. A touch-up treatment may be performed 4 weeks after the initial treatment if optimal midface augmentation has not been obtained. Optimal midface augmentation is defined as the best possible aesthetic result that can be obtained for an individual study participant, as agreed upon by the treating investigator and subject.

Subjects assigned to the Control Group in Group B will not receive treatment at baseline but will return for routine follow-up for 12 months. At month 6 visit, subjects in control group will be offered a treatment and an optional touch-up treatment.

Evaluation of effectiveness

 GALDERMA	<small>Title</small> 43CH1507 Perlane Lido midface study protocol	<small>Doc id</small> MA-30843
---	--	-----------------------------------

Effective date: 2016-09-07 11:57

Midface fullness will be assessed using a separate four-grade MMVS with photoguides for the right and left side **CCI** [REDACTED] by the blinded evaluator, at screening, baseline, **CCI** 6, **CCI** [REDACTED] months in Group A and Treatment Group, and at screening, baseline, **CCI** 6 months, **CCI** [REDACTED] in Control Group.

CCI [REDACTED]

Evaluation of safety

Information regarding AEs will be collected continuously during the study. **CCI** [REDACTED]

CCI [REDACTED]

Version: 4.0

 GALDERMA	Title 43CH1507 Perlane Lido midface study protocol	Doc id MA-30843
--	--	---------------------------

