4.7 Schedule of events

Table 1. Schedule of Events for Group A and Treatment Group

	Group A and Treatment Group					
	Screening ^a	Baseline ^a / Initial treatment	Follow-up / Optional Touch-up	Follow-up ^b	Follow-up	Final visit / Early termination
	D-21 to D1	D1	4W(±3d) after randomization	4W(±3d) after touch-up	3M(±1w), 6M(±1w) and 9M (±2w) after last treatment	12M (±2w) after last treatment
Informed consent	X					
Height, Demography	X					
Weight	X	X	X	X	X	X
Medical history & concurrent diseases	X	X				
Concomitant medication/procedures	X	X	X	X	X	X
Vital signs		X ^c				
Laboratory tests	X		X		X ^c	X ^f
ECG	X					
Pregnancy test		X ^c	X ^c			X
Inclusion and Exclusion criteria	X	X				
Randomization		X				
Treatment		X	X			
MMVS (Blinded Evaluator)	X	X ^c			X	X
CCI						
Photography		X ^c	X ^{c, d}	X	X	X

Device deficiencies		X	X			
Assessment of AE	X	X	X	X	X	X
Study termination						X

a) Screening visit and baseline visit can be combined to one visit if feasible.

b) Only for subject receive touch-up treatment.

c) Prior to treatment, if treat performed.

CCI

e) Only performed at 6M.

f) Only performed at early termination if termination occurs before 6 months visit after last treatment

Table 2. Schedule of Events for Control Group

Activity	Control Group									
	Screening ^a	Baseline ^a	Follow-up	Follow-up	Follow-up /Treatment	Follow-up /Optional Touch-up	Follow-up ^b	Follow-up	Final visit / Early termination	
	D-21 to 1	D1	4W(±3d) after randomization	3M (±1w) after randomization	6M(±1w) after randomization	4W(±3d) after 6M treatment	4W(±3d) after touch-up	3M (±1w) after last treatment	6M (±1w) after last treatment	
Informed consent	X									
Height, Demography	X									
Weight	X	X	X	X	X	X	X	X	X	
Medical history & concurrent diseases	X	X								
Concomitant medication/procedures	X	X	X	X	X	X	X	X	X	

Vital signs		X			X ^c					
Laboratory tests	X				X ^c	X				X
ECG	X									
Pregnancy test		X			X ^c	X ^c				X
Inclusion and Exclusion criteria	X	X								
Randomization		X								
Treatment					X	X				
MMVS (Blinded Evaluator)	X	X		X	X ^c			X		X
CCI										
Photography		X	X ^d	X	X ^c	X ^c	X	X		X
CCI										
Device deficiencies					X	X				
Assessment of AE	X	X	X	X	X	X	X	X		X
Study termination										X

a) Screening visit and baseline visit can be combined to one visit if feasible.

b) Only for subject receive touch-up treatment.

c) Prior to treatment, if treat performed.

CCI

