4.8.1.2 Baseline (D1)

- Weight
- Medical history/concurrent diseases
- Vital signs (pulse rate, blood pressure, respiratory rate, axillary temperature)
- Inclusion and exclusion criteria
- Pregnancy test for childbearing potential women
- Photography (before injection)
- Randomization
- MMVS (by Blinded Evaluator CCI [REDACTED])
- Treatment
- CCI [REDACTED]
- Concomitant medications and treatments
- Device deficiencies
- AE since last visit

4.8.1.3 4W ($\pm 3d$) after randomization Follow-up/Optional Touch-up

- Weight
- Photography (before injection)
- CCI [REDACTED]
- CCI [REDACTED]
- Pregnancy test for childbearing potential women
- Treatment (optional)
- CCI [REDACTED]
- CCI [REDACTED]
- Concomitant medications and treatments

	
Title 43CH1507 Perlane Lido midface study protocol 
	
Doc id MA-30843 

--	---	--

2016-09-07 11:57

Effective date:

Effective

Version: 4.0

- Device deficiencies
- AE since last visit
- Laboratory tests (haematology and serum chemistry)

4.8.1.4 4W ($\pm 3d$) after touch-up Follow-up (only for subjects who received touch-up)

- Weight
- Photography
- CCI
-
-
-
- Concomitant medications and treatments
- AE since last visit

4.8.1.5 3M ($\pm 1w$), 6M ($\pm 1w$) and 9M ($\pm 2w$) after last treatment Follow-up

- Weight
- Photography
- MMVS (by Blinded Evaluator CCI [REDACTED])
- CCI
-
- Concomitant medications and treatments
- AE since last visit
- Laboratory tests (Only performed at 6M)

4.8.1.6 12M ($\pm 2w$) after last treatment Final visit or Early termination

- Weight
- Photography
- MMVS (by Blinded Evaluator CCI [REDACTED])
- CCI
-
- Pregnancy test for childbearing potential women
- Concomitant medications and treatments
- AE since last visit
- Laboratory tests (Only performed at early termination if termination occurs before 6 months visit after last treatment)
- Study termination

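### Eligibility is not re-checked before the controls' first injection at Month 6, so a few Day 1 exclusions are not applied when the device is first used

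*Protocol*

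**What the plan says.** Protocol 4.1 gives the Control Group no treatment at baseline and then provides: "At month 6 visit, subjects in control group will be offered a treatment and an optional touch-up treatment". The same paragraph says that controls "will return for routine follow-up for 12 months".

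In Table 2 of Protocol 4.7 (Control Group), the rows "Inclusion and Exclusion criteria" and "Medical history & concurrent diseases" are ticked at Screening and Baseline and nowhere else. The Month 6 visit list in 4.8.2.5 shows neither. In the Treatment Group, 4.8.1.2 lists "Inclusion and exclusion criteria" and medical history at the same visit as the first injection.

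For controls at Month 6, the plan schedules weight, vital signs, laboratory tests, a pregnancy test, concomitant medication and adverse event (AE) review. Footnote c of Table 2 places vital signs, laboratory tests and the pregnancy test before the injection: "Prior to treatment, if treat performed". That footnote also foresees that some controls will not be injected.

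After Month 6, all control visits are timed from a treatment. The first is "4W(±3d) after 6M treatment" and the last is "6M (±1w) after last treatment".

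**The concern.** Several exclusion criteria in 5.3 are look-back windows that end at treatment, and others describe a state that can arise at any time. For a treated subject they are applied on the day of injection. For a control they are applied on Day 1, about six months before there is any injection to protect against. A control could then receive a first injection in a state that would have barred her on Day 1, and the site would have followed its visit schedule exactly.

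The stake is subject safety at first device exposure. There is also a small effect on the safety data. SAP 3.4.2 and Table A 34 combine the controls' AEs after their Month 6 injection with those of the Treatment Group, so the combined column would include subjects whose eligibility was not confirmed at first injection.

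**Working it through.** **The plan's own figures.** Allocation: 148 × 1/4 = 37 controls and 148 × 3/4 = 111 treated, as stated in the Synopsis. Duration, with one month = 365.25/12 = 30.44 days: a control with touch-up has 21 days of screening + 6 months + 28 days + 6 months. That is 12 + 49/30.44 = 13.6 months, or 14.2 if the 7 + 3 + 7 days of late windows are all used. This agrees with the roughly 14 months in 4.3.

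**Gap from last check to first injection** (6 months = 183 days, 3 months = 91 days).
- Treatment Group: 0 days (4.8.1.2).
- Control Group: 183 ± 7 = 176 to 190 days.
- The 3-month window of exclusion 18 opens at 176 − 91 = day 85 to 190 − 91 = day 99. It lies wholly after the last eligibility check.

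**Which exclusions are carried to Month 6 by other text?**

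| Exclusion (5.3) | Other text that applies at Month 6 | Gap |
|---|---|---|
| 4, 7, 8, 19, 26 (procedures, fillers, neurotoxin, retinoids, other studies) | Broadly prohibited during the study by 4.6 | No withholding rule if breached; 4.6 records a deviation and the subject continues |
| 17 (bleeding disorder, anticoagulants, platelet inhibitors) | Two-week restriction in 4.6; IFU bars use with bleeding disorders or anticoagulants | Little |
| 18, chemotherapy and immunosuppressive or immunomodulatory part | Prohibited by 4.6 | As in the first row |
| 18, corticosteroid part | 4.6 bans long-term use only and leaves other use to the investigator | A short course within 3 months is excluded on Day 1 and allowed before Month 6 |
| 15 (autoimmune or connective tissue disease) | AE review; not named in the IFU text supplied | No rule |
| 3, 16 (anaphylaxis history; keloid or healing disorder) | AE review; not named in the IFU text supplied | No rule |
| 23 (pregnancy) | Test before injection (Table 2, 8.2); 8.4.7 keeps the subject in follow-up; the IFU says only that the product is untested in pregnancy | Consequence of a positive test is implied, not written |

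**Follow-up of an uninjected control.** Four visits follow Month 6 in Table 2: 4 weeks after the Month 6 treatment, 4 weeks after touch-up, and 3 and 6 months after last treatment. All 4 are dated from a treatment and 0 from randomization. The last visit with a computable date is Month 6, which leaves 12 − 6 = 6 months of the follow-up in 4.1 without dates. The documents do not give the share left uninjected. If it were 5%, 10% or 20% (assumption), 37 × 0.05 = 1.9, 37 × 0.10 = 3.7 or 37 × 0.20 = 7.4, so about 2, 4 or 7 controls.

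**Pooled safety data.** If every treated subject and every control is injected, 37/148 = 25% of the combined column had no scheduled eligibility check at first injection.

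**The case against.** A reader might infer that the plan has no rule at all for withholding the Month 6 injection. The documents do not support that. The signed agreement page makes the IFU part of the basis of the study. The IFU bars use in lidocaine or amide-anaesthetic hypersensitivity, in bleeding disorders or with thrombolytics or anticoagulants, and in active disease at or near the site. Section 4.6 restricts anticoagulants and platelet inhibitors for two weeks before any treatment. Treatment is only offered, investigators are chosen for their skill with fillers (2.5), and 5.5 lets them withdraw a subject at their discretion, so declining an elective injection is a lesser step.

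The remaining gaps can also be played down. A new disease would surface in the AE review at every visit, and a steroid course in the medication review. No document shows that a finished short course makes injection unsafe; the IFU itself mentions a short course when managing a reaction. The purpose of a pregnancy test before injection is plain. The Treatment Group has no eligibility re-check before its touch-up either. An uninjected control has already given the primary endpoint and has no device exposure to follow. Parts of Table 2 and 4.8.2.5 are redacted and the flow chart is not visible.

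Much of this stands. It removes any absolute claim, and taken alone the pregnancy and follow-up parts are drafting detail. It does not remove the core. The two relevant rows of Table 2 are legible and end at Baseline. A touch-up about 4 weeks after a full check differs from a first exposure about 6 months after one. Reviewing AEs and medication shows the finding to the investigator without saying what follows from it. Exclusion 18 and 4.6 give different answers to the same steroid course, depending only on the arm.

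**Conclusion.** The point holds in a limited form. Controls receive their first injection 176 to 190 days after their last scheduled eligibility check, while treated subjects are checked at the injection visit. Existing safeguards cover most risks, but exclusions 3, 15 and 16 and the short-course part of 18 are not applied at Month 6. For prohibited use, 4.6 documents a deviation and does not stop the injection.

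The size is small. At most about 37 controls are concerned. The documents give no rate for exclusions newly arising by Month 6, so no number affected is claimed. A reader might also fear for the primary comparison, but the control score on the Medicis Midface Volume Scale (MMVS) at Month 6 is taken before the injection, so the primary endpoint is unaffected. Nor is an uninjected control left without follow-up on paper: 4.1 gives 12 months and a final or early-termination visit exists. Only the dates are missing.

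The conclusion assumes that no redacted item or the unseen flow chart adds an eligibility check at Month 6; the legible rows of Table 2 speak against it.

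**What to change.** 1. In the 6M column of Table 2 and in 4.8.2.5, add a re-check of the safety-relevant exclusions (at least nos. 3, 15, 16, 18 and 23) and an update of medical history, to be done with the AE and medication review before injection.
2. State that a control who meets one of these exclusions, including a positive pregnancy test, is not injected but stays in follow-up.
3. As a secondary clarification, date the remaining visits of an uninjected control from randomization, for example Months 9 and 12, in line with the 12 months in 4.1.

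The cost is a short protocol amendment with ethics committee approval (12.3), two ticks at one visit, one item in the electronic case report form, and a two-visit branch for uninjected controls. The re-check draws on information already collected at that visit. The downside is that a few of the roughly 37 controls may not receive the optional injection.

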4.2 Number of Subjects

The study will be performed at approximately 5 sites in China and approximately 168 subjects will be enrolled.

4.3 Duration of Subject Participation

The total duration for each subject will be approximately 14 months.

4.4 Randomization and blinding

4.4.1 Randomization

Approximately 148 subjects will be randomized in a 3:1 ratio to treatment with Perlane-Lido or to no treatment. Before starting the study, a computer generated randomization list will be prepared under the supervision of a designated statistician.

Each subject will be assigned a subject number as they arrive for the treatment visit. For group B, randomization will be assigned via the eCRF system. At the time for randomization, the subject's initials, date of randomization, subject number, randomized treatment, and the signature of the Investigator must be documented in a randomization log. The treatment information will be kept by the Treating Investigator during the study not to be disclosed to the Blinded Evaluator.

4.4.2 Blinding

Only the evaluator will be blinded, both treating investigator and subjects will be open-labelled.

The Blinded Evaluator shall not be allowed to retrieve study supplies or to be present during opening of the study supplies or injections. The Treating Investigator is not allowed to discuss treatments with the blinded evaluator or the subjects. All documents with information on study products shall be kept in a separate binder not available to the blinded evaluator.

4.4.3 Emergency unblinding

Not applicable as the Treating Investigator is unblinded.

4.5 Medical history

History of surgical events and medical conditions that are judged as relevant by the Investigator shall be documented in the eCRF using medical terminology.

4.6 Concomitant Medication, Treatment, and Procedure

Except as noted below, concomitant medications or other treatments or procedures may be utilized when the PI or his/her authorized designee considers it medically necessary.

Information regarding any use of concomitant medications, including over-the-counter medications administered during the study is to be recorded in the eCRF. The generic name or the trade name of all concomitant medication or a description of the procedure and the reason for its use shall be documented in the eCRF.

 GALDERMA	Title 43CH1507 Perlane Lido midface study protocol	Doc id MA-30843
--	--	---------------------------

2016-09-07 11:57

Effective date:

Effective

Version: 4.0

The following medications, treatments, and procedures are restricted or prohibited during the study:

- Anticoagulants or inhibitors of platelet aggregation (e.g. aspirin or other non-steroidal anti-inflammatory drugs [NSAIDs]), Omega-3, or Vitamin E should not be used within two weeks before treatment to avoid increased bruising or bleeding at injection sites.
- Lidocaine should be used with caution in patients receiving other local anesthetics or agents structurally related to amide-type local anesthetics e.g., certain antiarrhythmics, since the systemic toxic effects can be additive.
- Concomitant treatment with chemotherapy, immunosuppressive agents, immunomodulatory therapy (e.g., monoclonal antibodies) is prohibited.
- Long term concomitant treatment with systemic or topical (facial) corticosteroids is prohibited (inhaled corticoids are allowed). Corticosteroids should be used with caution and should be adjudged as necessary by the Investigator.
- Use of systemic or topical (facial) retinoic acid is prohibited.
- Facial tissue augmenting therapy, contouring or revitalization treatment with fillers, lifting threads, permanent implant, mesotherapy, radiofrequency, ultrasound, cryotherapy, fat-injection, neurotoxin, laser or light treatment, chemical peeling or dermabrasion are prohibited.
- Planned surgery including aesthetic facial surgical therapy or facial liposuction, sinus surgery or dental root surgery, or tattoo in the area to be treated is prohibited.
- Participation in any other clinical study is prohibited

If a subject has used any of the above prohibited medications or performed any of the above prohibited procedures, a protocol deviation will be documented. The subject should continue in the study for the scheduled follow-up visits.

 GALDERMA	Title 43CHI507 Perlane Lido midface study protocol	Doc id MA-30843
---	--	----------------------------------

4.7 Schedule of events

Table 1. Schedule of Events for Group A and Treatment Group

	Group A and Treatment Group					
	Screening ^a	Baseline ^a / Initial treatment	Follow-up / Optional Touch-up	Follow-up ^b	Follow-up	Final visit / Early termination
	D-21 to D1	D1	4W(±3d) after randomization	4W(±3d) after touch-up	3M(±1w), 6M(±1w) and 9M (±2w) after last treatment	12M (±2w) after last treatment
Informed consent	X					
Height, Demography	X					
Weight	X	X	X	X	X	X
Medical history & concurrent diseases	X	X				
Concomitant medication/procedures	X	X	X	X	X	X
Vital signs		X ^c				
Laboratory tests	X		X		X ^c	X ^f
ECG	X					
Pregnancy test		X ^c	X ^c			X
Inclusion and Exclusion criteria	X	X				
Randomization		X				
Treatment		X	X			
MMVS (Blinded Evaluator)	X	X ^c			X	X
CCI						
Photography		X ^c	X ^{c, d}	X	X	X

Device deficiencies		X	X			
Assessment of AE	X	X	X	X	X	X
Study termination						X

a) Screening visit and baseline visit can be combined to one visit if feasible.

b) Only for subject receive touch-up treatment.

c) Prior to treatment, if treat performed.

CCI

e) Only performed at 6M.

f) Only performed at early termination if termination occurs before 6 months visit after last treatment

Table 2. Schedule of Events for Control Group

Activity	Control Group									
	Screening ^a	Baseline ^a	Follow-up	Follow-up	Follow-up /Treatment	Follow-up /Optional Touch-up	Follow-up ^b	Follow-up	Final visit / Early termination	
	D-21 to 1	D1	4W(±3d) after randomization	3M (±1w) after randomization	6M(±1w) after randomization	4W(±3d) after 6M treatment	4W(±3d) after touch-up	3M (±1w) after last treatment	6M (±1w) after last treatment	
Informed consent	X									
Height, Demography	X									
Weight	X	X	X	X	X	X	X	X	X	
Medical history & concurrent diseases	X	X								
Concomitant medication/procedures	X	X	X	X	X	X	X	X	X	

Vital signs		X			X ^c					
Laboratory tests	X				X ^c	X				X
ECG	X									
Pregnancy test		X			X ^c	X ^c				X
Inclusion and Exclusion criteria	X	X								
Randomization		X								
Treatment					X	X				
MMVS (Blinded Evaluator)	X	X		X	X ^c			X		X
CCI										
Photography		X	X ^d	X	X ^c	X ^c	X	X		X
CCI										
Device deficiencies					X	X				
Assessment of AE	X	X	X	X	X	X	X	X		X
Study termination										X

a) Screening visit and baseline visit can be combined to one visit if feasible.

b) Only for subject receive touch-up treatment.

c) Prior to treatment, if treat performed.

CCI

 GALDERMA	Title 43CH1507 Perlane Lido midface study protocol	Doc id MA-30843
--	---	----------------------------------

4.8 Visits

4.8.1 Visits for Group A and Treatment Group

4.8.1.1 Screening (D-21 to D1)

- Informed consent
- Demography (Initials, Date of birth, Gender and Ethnic origin)
- Height and Weight
- Screening laboratory tests (haematology and serum chemistry)
- ECG
- Inclusion and exclusion criteria
- MMVS (by Blinded Evaluator CCI [REDACTED])
- Medical history/concurrent diseases
- Concomitant medications and treatments
- AE during the visit

4.8.1.2 Baseline (D1)

- Weight
- Medical history/concurrent diseases
- Vital signs (pulse rate, blood pressure, respiratory rate, axillary temperature)
- Inclusion and exclusion criteria
- Pregnancy test for childbearing potential women
- Photography (before injection)
- Randomization
- MMVS (by Blinded Evaluator CCI [REDACTED])
- Treatment
- CCI [REDACTED]
- Concomitant medications and treatments
- Device deficiencies
- AE since last visit

4.8.1.3 4W ($\pm 3d$) after randomization Follow-up/Optional Touch-up

- Weight
- Photography (before injection)
- CCI [REDACTED]
- CCI [REDACTED]
- Pregnancy test for childbearing potential women
- Treatment (optional)
- CCI [REDACTED]
- CCI [REDACTED]
- Concomitant medications and treatments

	
Title 43CH1507 Perlane Lido midface study protocol 
	
Doc id MA-30843 

--	---	--

2016-09-07 11:57

Effective date:

Effective

Version: 4.0

- Device deficiencies
- AE since last visit
- Laboratory tests (haematology and serum chemistry)

4.8.1.4 4W ($\pm 3d$) after touch-up Follow-up (only for subjects who received touch-up)

- Weight
- Photography
- CCI
-
-
-
- Concomitant medications and treatments
- AE since last visit

4.8.1.5 3M ($\pm 1w$), 6M ($\pm 1w$) and 9M ($\pm 2w$) after last treatment Follow-up

- Weight
- Photography
- MMVS (by Blinded Evaluator CCI [REDACTED])
- CCI
-
- Concomitant medications and treatments
- AE since last visit
- Laboratory tests (Only performed at 6M)

4.8.1.6 12M ($\pm 2w$) after last treatment Final visit or Early termination

- Weight
- Photography
- MMVS (by Blinded Evaluator CCI [REDACTED])
- CCI
-
- Pregnancy test for childbearing potential women
- Concomitant medications and treatments
- AE since last visit
- Laboratory tests (Only performed at early termination if termination occurs before 6 months visit after last treatment)
- Study termination

